## **9.0 Study Drug Exposure and Compliance**

### **9.1 Study Drug Exposure**

Summary of study drug exposure and study drug compliance will be provided for each treatment arm for ITT\_1 and ITT\_2.

Study drug exposure (days) will be summarized using the sample size, mean, standard deviation, minimum, median and maximum for each treatment part. Study drug exposure will be summarized as follows:

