8.1.3.3 Study Drug Exposure and Compliance

Exposure to study drug will be summarized for the Safety Populations in Period 1 and Period 2. The exposure to study drug (days) will be summarized with the mean, standard deviation, median, and range for each treatment group. The exposure to study drug is defined as the difference between the dates of the first and last doses of the study drug plus 1 day. Study drug compliance will also be summarized for each treatment group. The compliance is defined as the number of tablets taken (i.e., the difference between the number of tablets dispensed and the number of tablets returned) during the subject's

participation in the study divided by the number of tablets a subject is supposed to take each day times the length of time that the subject was in the Treatment Phase of the study.

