### **5.0 Analysis Populations**

#### **5.1 Analysis Populations**

##### **Intent-to-Treat (ITT) Population**

An ITT population will be defined for each period and be used for the efficacy analyses.

---

- The ITT Population in Period 1 (ITT\_1) is defined as all subjects who are randomized at Day 1.
- The ITT Population in Period 2 (ITT\_2) is defined as all subjects who are re-randomized at the entry of Period 2.

For efficacy analyses, subjects included in the ITT populations will be analyzed as randomized. If a subject is randomized or re-randomized in the wrong strata, the subject will be analyzed according to the actual strata that subject belongs to.

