### **Safety Population**

A Safety population will be defined for each period and be used for safety analyses.

- The Safety Population in Period 1 (Safety\_1) is defined as all subjects who are randomized and receive at least one dose of study drug in Period 1.
- The Safety Population in Period 2 (Safety\_2) is defined as all subjects who are re-randomized at the entry of Period 2 and receive at least one dose of study drug in Period 2.

For the Safety populations, subjects are assigned to a treatment group based on the "as treated" treatment group. In the case where the subject received more than one treatment, the "as treated" is determined by the dosage that a patient received the most during a period.

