## **11.0 Safety Analysis**

### **11.1 General Considerations**

Safety analyses will include adverse events, laboratory, and vital sign measurements. Safety summaries will be provided using the safety population in each period. Comparison between each upadacitinib group and placebo group will be performed for change from baseline laboratory and vital sign parameters in the Safety\_1 Population, using one-way ANOVA.

Missing safety data will not be imputed.

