### **11.2.1.7 Adverse Events by 100 Patient Years**

TEAEs will be summarized by event rate per 100 subject years, defined as

$$100 * (\text{Number of TEAEs}) / (\text{Total Patient Years})$$

where total patient years is defined as the sum of the study drug exposure (defined in Section 9.1) of all subjects normalized by 365.25, and rounded to 1 decimal place. Event rate (per 100 patient years) for AEs of special interest will also be summarized for the combined safety analysis of Period 1 and Period 2.

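### SAP 9.1 summarises exposure by ITT arm where the protocol specifies the Safety Populations, and the grouping behind the Period 2 patient-years is left open

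*SAP*

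**What the plan says.** **Population for exposure.** Protocol 8.1.3.3: "Exposure to study drug will be summarized for the Safety Populations in Period 1 and Period 2". SAP 9.1: "Summary of study drug exposure and study drug compliance will be provided for each treatment arm for ITT"; the sentence goes on to name ITT_1 and ITT_2. SAP 12.1, the list of departures from the protocol, is silent on this.

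**Formula.** In SAP 9.1, Period 2 exposure is the last Period 2 dose date minus the first, plus one day. Nothing stops the count at rescue. SAP 9.2, by contrast, ends Period 2 compliance on the day before the first rescue dose.

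**Grouping.** In SAP 5.1, for efficacy, "subjects included in the ITT populations will be analyzed as randomized"; no other arm assignment is given for the ITT populations. The Safety populations are grouped as treated, and for a subject with more than one treatment the group "is determined by the dosage that a patient received the most during a period".

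**Event rates.** SAP 11.1: "Safety summaries will be provided using the safety population in each period". SAP 11.2.1.7 gives the denominator: "where total patient years is defined as the sum of the study drug exposure (defined in Section 9.1) of all subjects", divided by 365.25. It names neither ITT arms nor Safety groups. It adds combined Period 1 and 2 rates for events of special interest, again with no grouping.

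**Rescue.** Under protocol 5.2.3.4, Period 2 subjects on placebo, 7.5 mg or 15 mg switch to 30 mg at their first response below EASI 50 from the Week 20 visit onwards, and stay on it to the end.

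**The concern.** The protocol and SAP name different populations for the same table, and the difference is not logged. The later date of the supplied protocol does not explain it: the SAP cites the 07 June 2017 version, but the itemised changes in the 30 August 2017 amendment (Appendix Q) touch only events of special interest.

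In Period 2 the choice matters. An early rescue changes a subject's majority dose but not the randomised arm. Two consequences follow, of different certainty. The ITT_2 exposure table will report time on 30 mg as exposure of a lower-dose or placebo arm. The Period 2 and combined-period event rates may also be formed from events in one set of subjects and patient-years from another, because the denominator points to a section whose only named populations are ITT. On that reading, placebo rates would come out too low and 30 mg rates too high.

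**Working it through.** The documents state no exposure total, rescue rate or event rate, so there is no figure of the plan's own to reproduce.

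**Inputs.** 40 subjects per Period 1 group (SAP 4.3), so about 20 per Period 2 arm at 1:1 without dropout. Period 2 lasts 72 weeks, Week 16 to Week 88 (protocol 5.1). The rescue share *f* is assumed and varied from 10% to 75%.

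**Step 1: who changes group.** For a subject who completes Week 88, rescue at Week *v* gives *v* − 16 weeks on assigned treatment and 88 − *v* weeks on 30 mg.

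| Rescue visit | Weeks on assigned treatment | Weeks on 30 mg | Majority dose |
|---|---|---|---|
| 20 | 4 | 68 | 30 mg |
| 24 | 8 | 64 | 30 mg |
| 32 | 16 | 56 | 30 mg |
| 40 | 24 | 48 | 30 mg |
| 52 | 36 | 36 | tie, no rule |
| 64 | 48 | 24 | assigned |
| 76 | 60 | 12 | assigned |

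Rescue up to Week 40 therefore moves a completer to 30 mg in Safety_2, while ITT_2 leaves the subject in place.

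**Step 2: what the ITT_2 table contains.** Full Period 2 exposure is 72 × 7 / 365.25 = 1.38 patient-years per subject, or 27.6 per arm of 20. A subject rescued at Week 20 contributes 68 × 7 / 365.25 = 1.30 of those on 30 mg. In a placebo arm:

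- *f* = 10%: 2 × 1.30 = 2.6 of 27.6 patient-years are 30 mg time (0.10 × 68/72 = 9.4%).
- *f* = 60%: 12 × 1.30 = 15.6 of 27.6 (0.60 × 68/72 = 57%).

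This step does not depend on how SAP 11.2.1.7 is read.

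**Step 3: event rates if Safety-group events are divided by ITT-arm exposure.** The factor relative to the matched Safety-group rate is Safety patient-years divided by ITT patient-years. For a placebo arm it is 20(1 − *f*)/20 = 1 − *f*. For the paired 30 mg arm, which receives the moved subjects, it is 20(1 + *f*)/20 = 1 + *f*.

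| *f* | ITT_2, each arm | Safety_2 placebo | Safety_2 30 mg | Factor, placebo | Factor, 30 mg |
|---|---|---|---|---|---|
| 10% | 27.6 | 24.8 | 30.4 | 0.90 | 1.10 |
| 25% | 27.6 | 20.7 | 34.5 | 0.75 | 1.25 |
| 40% | 27.6 | 16.6 | 38.6 | 0.60 | 1.40 |
| 60% | 27.6 | 11.0 | 44.2 | 0.40 | 1.60 |
| 75% | 27.6 | 6.9 | 48.3 | 0.25 | 1.75 |

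If both parts use the Safety_2 group, the factor is 1.00 by construction. Among completers the factor is the same for any rescue up to Week 40, since the whole 72 weeks move with the subject.

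**Step 4: is the range plausible?** As a rough guide only, take the SAP 4.3 planning figures as normal and assume the Week 16 distribution persists at Week 20. With the placebo mean of 35 and SD 40, the share below EASI 50 is Φ((50 − 35)/40) = Φ(0.375) = 65%, which would apply to PBO/PBO. With the 30 mg mean of 70 it is Φ((50 − 70)/40) = Φ(−0.5) = 31%, which would apply to UPA 30/PBO if the response were fully retained.

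**Step 5: Period 1.** There is no 30 mg rescue, so ITT_1 and Safety_1 differ only through undosed or wrongly dosed subjects, and the undosed add no exposure.

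**The case against.** A reader might infer that the SAP prescribes mismatched numerators and denominators, with Period 2 rates off by some 60% as a matter of course. The documents do not support that, for four reasons.

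- The cross-reference in SAP 11.2.1.7 is to how exposure is defined. It can be read as borrowing only the subject-level formula, with the safety population of SAP 11.1 applied to both parts of the rate. That reading is consistent and arguably the more natural one.
- SAP Table 1 gives ITT_2 and Safety_2 the same eight codes. Of the six rescue-eligible arms, only UPA 30/PBO and PBO/PBO have a 30 mg destination. For 7.5/7.5, 7.5/PBO, 15/15 and 15/PBO the move has no defined target.
- SAP 9.1 also plans upadacitinib exposure by dose level across periods, and SAP 11.2 plans TEAE summaries by dose level of monotherapy. Both separate time by dose taken, which suits rescued subjects better than either grouping.
- The size depends wholly on an assumed rescue share and no dropout.

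These points reduce the mismatch from a stated error to a risk created by ambiguous wording. They do not remove the rest. The population conflict and its absence from SAP 12.1 are plain, and Step 2 holds on any reading. The by-dose summaries cover upadacitinib only, so they give no placebo exposure or placebo event rate by treatment actually taken. The missing Table 1 categories are a further gap in the Safety_2 grouping, since the majority-dose rule sends subjects to groups that do not exist.

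**Conclusion.** The point holds as an unlogged conflict over the exposure population, together with an open choice of denominator for Period 2 and combined-period event rates.

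Certain: protocol 8.1.3.3 and SAP 9.1 differ, and ITT_2 exposure is not cut at rescue, so it mixes 30 mg time into the placebo, 7.5 mg and 15 mg arms.

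Conditional: if patient-years are taken by ITT arm, rates are multiplied by (1 − *f*) on placebo and (1 + *f*) in the paired 30 mg arm. This assumes 20 per arm, completers only, and a share *f* rescued early. It is worked only for the two pairs with a Table 1 destination: UPA 30/PBO with UPA 30/UPA 30, and PBO/PBO with PBO/UPA 30. The range is 0.90 and 1.10 at 10% to 0.25 and 1.75 at 75%.

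The Period 1 placebo-controlled safety comparison is essentially untouched. The change is worth making because it settles a rule that now admits two answers, at little cost.

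**What to change.** - **SAP 9.1:** summarise exposure in Safety_1 and Safety_2, as the protocol says. If an ITT exposure table is kept as well, log it in SAP 12.1.
- **SAP 11.2.1.7:** state that patient-years come from the same subjects and treatment grouping as the TEAE counts in that table, including the combined-period rates.
- **SAP 5.1 and Table 1:** add Safety_2 categories for 7.5 mg and 15 mg Period 1 subjects whose majority Period 2 dose is 30 mg, and a rule for ties (nominally, rescue at Week 52).
- **Alongside:** present event rates by treatment actually taken, including placebo time before rescue. Matching the groups alone would still count pre-rescue time under the majority dose.

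The cost is SAP wording, a population flag, the extra group codes and one further set of rate tables. No new data are needed: the date of the first rescue dose is already required for compliance in SAP 9.2 and for the efficacy rule in SAP 10.1.5.

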#### **Period 1:**

For subjects who did not continue into Period 2:

- Date of last dose of study drug in Period 1 – Date of first dose of study drug in Period 1 + 1.

For subjects who continued into Period 2: the minimum of

- Date of first dose of study drug in Period 2 – Date of first dose of study drug in Period 1.
  - Date of last dose of study drug in Period 1 – Date of first dose of study drug in Period 1 + 1.
-

### **Period 2:**

- Date of last dose of study drug in Period 2– Date of first dose of study drug in Period 2 + 1.
- For interim analysis at Week 32, minimum of the above and (cutoff date – Date of first dose of study drug in Period 2 + 1).

Additional summaries of upadacitinib exposures by dose level will also be performed including exposure to each dose level across periods.

## **9.2 Compliance**

Treatment compliance (TC) will be summarized for each treatment group in each period. The treatment compliance is defined as the number of tablets actually taken by the subject divided by the number of tablets planned to be taken by the subject during the double-blind treatment period of the study. Of note, the compliance in Period 2 will be summarized up to the date prior to the first dose of rescue. Based on a daily dose of one tablet for the study drug, TC will be calculated using the following formula:

$$TC = \frac{\text{number of tablets taken}}{\text{number of days from first to last dose of blinded study drug}} \cdot 100\%$$

## **10.0 Efficacy Analysis**

### **10.1 General Considerations**

Efficacy analyses will be carried out in ITT\_1 and ITT\_2, respectively for Periods 1 and 2. Pairwise comparisons of each upadacitinib treatment group versus placebo will be performed in Period 1. Descriptive summaries will be provided for all treatment groups in Period 2.

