5.6 Discussion and Justification of Study Design

5.6.1 Discussion of Study Design and Choice of Control Groups

ABT-494 (upadacitinib) is a potent JAK1 selective inhibitor. The proposed study is a 88-week, randomized, double-blind, placebo-controlled study to compare multiple doses of ABT-494 versus placebo in moderate to severe AD adult patients that are candidates for systemic therapy. In order to assess the potential of ABT-494 to benefit patients with AD, patients with moderate to severe disease (baseline EASI \geq 16, BSA of \geq 10% and an IGA score \geq 3) will be enrolled and the mean percent change from Baseline in EASI score for different doses of ABT-494, compared to placebo will be assessed. The 16-week therapy (Period 1) is generally accepted as the timeframe during which an effective treatment would be expected to produce clinical benefit in AD. The 72-week double-

blind treatment period (Period 2) is to evaluate more long-term safety and efficacy of repeated administration of ABT-494 and to evaluate potential loss of response in AD subjects who have completed Period 1.

Placebo has been selected as the appropriate control group since, as discussed in Section 3.2, there is a lack of approved systemic therapies for moderate to severe AD, especially for long-term use.

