#### **4.2 Design Diagram**

This is an 88-week Phase 2b, randomized, double-blind, parallel-group, placebo-controlled multicenter study of safety and efficacy of upadacitinib in adult subjects with moderate to severe AD.

The duration of the study will be up to 88 weeks and will include a 35-day maximum screening period, a 16-week double-blind treatment period (Period 1) and a 72-week double-blind treatment period (Period 2). In addition, a 30-day follow-up visit (or phone

---

call if a visit is not possible) should occur to determine the status of any ongoing AEs or serious adverse events (SAEs), or the occurrence of any new AEs/SAEs.

**Period 1:** A 16-week double-blind, placebo-controlled treatment period during which subjects will be randomized in a 1:1:1:1 ratio to one of four treatment groups:

- Group 1: upadacitinib 7.5 mg once daily (QD) for 16 weeks
- Group 2: upadacitinib 15 mg QD for 16 weeks
- Group 3: upadacitinib 30 mg QD for 16 weeks
- Group 4: Matching Placebo for 16 weeks

Randomization will be stratified by geographic region (US/PR/Canada, EU/AUS, and Japan). Enrollment in Japan will be capped at 10% of subjects (4 subjects per group).

In Period 1, discontinuation from study drug will be mandatory for any subject with an Eczema Area and Severity Index (EASI) score worsening of 25% or more compared with their baseline EASI score at any 2 consecutive scheduled study visits from Week 4 to Week 12.

**Period 2:** a 72-week double-blind, placebo controlled treatment period during which subjects who complete Period 1 will be re-randomized at Week 16 within their original treatment group assignments to either upadacitinib or placebo into a 72-week double-blind, placebo controlled treatment period in a 1:1 ratio as shown in [Figure 1](#) (study design). Randomization will be stratified by geographic region and the improvement of EASI score by at least 75% (EASI 75 response) at Week 16. At the Week 16 visit, all subjects will be re-randomized as follows into Period 2:

- Group 1 in Period 1: upadacitinib 7.5 mg QD or matching placebo for 72 weeks
  - Group 2 in Period 1: upadacitinib 15 mg QD or matching placebo for 72 weeks
  - Group 3 in Period 1: upadacitinib 30 mg QD or matching placebo for 72 weeks
-

- Group 4 in Period 1: upadacitinib 30 mg QD or matching placebo for 72 weeks

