### **10.1.3 Analysis of Time to Event Variables**

For the time to event endpoints, the time to event will be calculated as:

- Time to first event (as observed) = [date of first event in Period 1] – [date of first study drug in Period 1] + 1;
- If a subject never attains an event in Period 1, then that subject's time to first achievement will be censored at the last visit where the variable was measured in Period 1.

Time to EASI 50/75/90 response and IGA "0" or "1" response will be evaluated for Period 1. Time to loss of EASI 50 response among those who were re-randomized as EASI 75 responders at Week 16 will be evaluated for Period 2.

Time to event variables will be analyzed by stratified log-rank test adjusting for stratification factors.

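### Period 2 re-randomises each active dose to continue or switch to placebo, but no continue-versus-withdraw estimate or interval is planned, and the SAP contradicts itself on whether Period 2 is tested

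*SAP*

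**What the plan says.** SAP 4.2 re-randomises Period 1 completers within their original "treatment group assignments to either upadacitinib or placebo into a 72-week double-blind, placebo controlled treatment period in a 1:1 ratio". The three active groups go to the same dose or placebo. The placebo group is different: "Group 4 in Period 1: upadacitinib 30 mg QD or matching placebo for 72 weeks", so it offers no withdrawal comparison. Re-randomisation is stratified by region and Week 16 EASI 75 (SAP 5.2).

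Protocol 5.6.1 gives Period 2 two purposes. It "is to evaluate more long-term safety and efficacy of repeated administration of ABT-494", and it is also meant "to evaluate potential loss of response in AD subjects who have completed Period 1".

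On analysis, SAP 10.1 states: "Pairwise comparisons of each upadacitinib treatment group versus placebo will be performed in Period 1". It continues: "Descriptive summaries will be provided for all treatment groups in Period 2". Protocol 8.1 says the same. SAP 10.1.3, however, states: "Time to loss of EASI 50 response among those who were re-randomized as EASI 75 responders at Week 16 will be evaluated for Period 2". It then states, without limiting the rule to Period 1: "Time to event variables will be analyzed by stratified log-rank test adjusting for stratification factors". Protocol 8.1.5.2 carries the same log-rank rule, and the protocol synopsis adds Kaplan-Meier methods.

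SAP 10.4 keeps both percent change in EASI from re-randomisation and time to loss of EASI 50 as secondary variables. SAP 10.5 evaluates primary and secondary variables at all scheduled visits, so Week 20 is summarised.

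**The concern.** Re-randomising within dose creates three matched pairs of arms that differ only in whether drug was continued. The difference within each pair is a randomised estimate of what stopping does, and it answers the loss-of-response question directly. Arm-by-arm summaries leave the reader to subtract by eye, with no measure of uncertainty, in arms of about 20.

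The one place where a comparison seems intended cannot be programmed as written. SAP 10.1 says Period 2 is descriptive and SAP 10.1.3 implies a test. If the test is run, its time origin, censoring and arms are undefined for Period 2, and it returns a p-value without an effect size.

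Timing adds to this. Period 1 results and a Week 32 interim analysis are produced while Period 2 is still running, so contrasts chosen after them could be seen as data-driven.

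**Working it through.** **1. The two analysis rules side by side.**
- SAP 10.1: comparisons in Period 1, description in Period 2.
- SAP 10.1.3: a log-rank test for time-to-event variables, one of which belongs to Period 2.
- Time formula in SAP 10.1.3: first event in Period 1 minus first dose in Period 1, plus 1. Censoring is at the last Period 1 measurement. There is no Period 2 counterpart.
- Strata: Week 16 EASI 75 takes one value among EASI 75 responders, so it does no work in this test.
- Intervals: SAP 10.1.1 and 10.1.2 promise 95% CIs for each upadacitinib group against placebo. SAP Table 1 has four Period 2 arms on placebo (7.5/PBO, 15/PBO, 30/PBO, PBO/PBO), so this wording would not identify the matched control even if extended to Period 2.

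**2. Why Week 20.** Drug rescue is first triggered at the Week 20 visit, and topical corticosteroids are permitted from Week 24 (Protocol 5.2.3.4). SAP 10.1.5 discards efficacy data from the day after the first rescue dose, then applies NRI or LOCF. Week 20 is therefore the only scheduled Period 2 visit that precedes all permitted rescue.

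**3. The plan's own power figures.** Inputs from SAP 4.3: 40 per group, SD 40, Week 16 means 35, 45, 60 and 70, two-sided 5%. Power = Φ(d / (SD·√(2/n)) − 1.96), with SD·√(2/n) = 40·√(2/40) = 8.944.
- 30 mg: d = 35, Φ(3.913 − 1.96) = 97.5% (noncentral t: 97.2%). Stated: 97%.
- 15 mg: d = 25, Φ(2.795 − 1.96) = 79.8% (noncentral t: 78.8%). Stated: 78%.

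The figures reproduce. They concern Week 16 only; no Period 2 precision is stated.

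**4. Precision of an added Week 20 contrast.** Half-width = t(0.975, 2n−2) · 40 · √(2/n), for percent change from Baseline in EASI. Assumptions: SD 40 carries over to Week 20, and 70% to 100% complete Period 1 (the documents give no rate).

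| Period 1 completion | Per dose, n per arm | Half-width | Pooled, n per arm | Half-width |
|---|---|---|---|---|
| 100% | 20 | 2.024 × 12.65 = 25.6 | 60 | 1.980 × 7.303 = 14.5 |
| 80% | 16 | 2.042 × 14.14 = 28.9 | 48 | 1.986 × 8.165 = 16.2 |
| 70% | 14 | 2.056 × 15.12 = 31.1 | 42 | 1.989 × 8.729 = 17.4 |

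Adjusting for the Week 16 value would shorten these by a factor √(1 − r²), where r is the Week 16 to Week 20 correlation, which is not given.

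**5. Time to loss of EASI 50.** Under a normal model with the planning means and SD, the EASI 75 share is 1 − Φ((75 − mean)/40): 22.7%, 35.4% and 45.0% at 7.5, 15 and 30 mg. Times 20 per arm, that is 4.5, 7.1 and 9.0 responders, or about 21 per arm pooled if all complete. Assume 20% loss on continued drug and 60% to 80% on withdrawal. The hazard-ratio CI extends a factor exp(1.96 · 2/√events) each way:
- 9 per arm (30 mg alone): 7.2 to 9 events, factor 4.3 to 3.7.
- 21 per arm (pooled): 16.8 to 21 events, factor 2.6 to 2.4.

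**The case against.** The best defence is that description was chosen deliberately. Protocol 8.1 and SAP 10.1 agree on it, this is a Phase 2b trial without multiplicity control (SAP 10.6), and Period 2 was not sized for comparison. That stands as a reason not to make significance claims. It does not argue against an interval, which spends no alpha.

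Several stronger readings are tempting, and the documents do not support them:
- **That nothing but description is planned.** SAP 10.1.3, read literally, assigns a log-rank test, and within-arm estimates are planned. What is missing is the between-arm estimate.
- **That the trial was built to measure withdrawal.** Loss of response is one of two Period 2 purposes, the study objectives do not mention it, and sample size rests on Week 16.
- **That Week 20 is ignored.** It has an analysis window and is summarised; only the contrast is absent.
- **That data after Week 20 are mostly imputed.** The planning means under a normal model put Φ((50−45)/40) = 55% of 7.5 mg and Φ((50−60)/40) = 40% of 15 mg subjects below EASI 50 at Week 16. Applying those shares to Week 20 assumes that they persist and ignores that only completers are re-randomised; the lower share is not a majority. The model is also crude: it puts 1 − Φ(0.75) = 23% of 30 mg subjects above 100% improvement.
- **That rescue spoils time to loss.** For Week 16 EASI 75 responders, falling below EASI 50 is both the event and the drug-rescue trigger. Rescue follows the event, so this endpoint can use visits after Week 20.

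Sparseness is a fair objection. Region by EASI 75 gives six strata for about 20 versus 20, and Japan supplies about 4 per Period 1 group. Full stratification within each dose, and hazard ratios for each dose, are not workable.

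**Conclusion.** The gap is real and limited. Neither document specifies a continue-versus-withdraw estimate or interval, although the randomisation provides one and Protocol 5.6.1 gives a reason to want it. Separately, SAP 10.1 and 10.1.3 conflict, and the Period 2 time-to-event analysis lacks an origin, a censoring rule and named arms.

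The pooled contrast is informative: a half-width of about 14.5 points is smaller than the 25 to 35 point differences from placebo assumed for 15 and 30 mg, if withdrawal effects are of that order. Dose by dose, 26 to 31 points is too wide to carry a conclusion. These sizes rest on SD 40 at Week 20, the assumed completion range and, for time to loss, the normal model and assumed loss rates. Primary Week 16 inference is unaffected. This is a cheap improvement to what Period 2 can conclude.

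**What to change.** 1. **Reconcile SAP 10.1 with 10.1.3.** State whether the log-rank test applies to Period 2. For time to loss of EASI 50, set the origin at the first Period 2 dose, censor at the last Period 2 EASI assessment, and compare each continued dose with its own dose/placebo arm.
2. **Add a lead analysis pooled over the three active doses with dose as a stratum**, reported as estimation without significance claims:
   - At Week 20, continue minus withdraw with 95% CI for percent change from Baseline in EASI, by ANCOVA with the Week 16 value as covariate, adjusted for dose, region and Week 16 EASI 75.
   - At Week 20, Mantel-Haenszel risk differences with 95% CI for EASI 50 and EASI 75, stratified by dose and Week 16 EASI 75, with region collapsed where sparse.
   - A dose-stratified hazard ratio with 95% CI for time to loss of EASI 50, dropping the EASI 75 stratum.
3. **Give per-dose Week 20 differences as supportive only**, and no per-dose hazard ratios.

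Fix these contrasts before Period 2 results are seen by treatment arm. The cost is SAP wording and a few extra tables. The downside is wide per-dose intervals, which must be shown as such. Conduct of the trial does not change.
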